5.6.2. Treatment Exposure

The treatment exposure to fasinumab and placebo SC doses will be calculated as:

- (Date of last administration of study drug - date of the first study drug administration after randomization) + 28

The duration of exposure will be summarized for each treatment group by descriptive statistics.

The number and percentage of patients randomized and exposed to double-blind study drug will be presented by specific time periods for each treatment group. The time periods of interest are specified as: ≥ 1 day, ≥ 29 days, ≥ 57 days, ≥ 85 days and ≥ 113 days.

5.6.3. Length of Study Observation/Participation

The length of the total study observation period (days) will be calculated as:

- (Date of last study visit [up to End of Follow-up Visit] – date of first study drug administration) + 1.

The length of the total study participation (days) will be calculated as:

- (Date of the last study visit [up to the EOS Phone Call] – date of the first study drug administration) + 1

The lengths of observations and total study participation will be summarized for each treatment group by descriptive statistics based on the SAF.

The number and percentage of patients with observation and participation periods will be presented by specific time periods. The time periods of interest are specified as: ≥ 1 day, ≥ 29 days, ≥ 57 days, ≥ 85 days, ≥ 113 days, ≥ 183 days, ≥ 253 days, ≥ 449 days.

5.6.4. Protocol Deviations

All important and minor protocol deviations have been collected and reviewed on an ongoing basis throughout the study as described in the Protocol Deviation Plan.

Protocol deviations will be summarized for patients incurring any important deviation by count and percentage, and patients incurring each type of important deviation by count and percentage for FAS.

A patient listing of all important and minor protocol deviations will be provided.

5.7. Analysis of Efficacy Data

5.7.1. Efficacy Analysis

The secondary efficacy endpoints of the study are:

- Change from baseline to week 16 in WOMAC pain subscale score
- Change from baseline to week 16 in WOMAC physical function subscale score

The following hypotheses will be tested:

- $H_{0,1}$: There is no treatment difference between fasinumab 1 mg Q4W and placebo in WOMAC pain subscale at week 16
- $H_{0,2}$: There is no treatment difference between fasinumab 1 mg Q4W and placebo in WOMAC physical function subscale at week 16

For the above hypotheses, the estimand is the difference in means between each fasinumab 1 mg Q4W and placebo in the change from baseline to week 16 in the WOMAC pain and physical function scores in the FAS, regardless of whether or not prohibited medication had been taken. Any data collected after discontinuing treatment will not be used in the main efficacy analysis, but used in a treatment policy sensitivity analysis.

Each of the secondary efficacy variables will be analyzed using a multiple imputation approach with mixed-effect model for repeated measure (MMRM) based on the FAS. For patients who permanently discontinued treatment due to lack of efficacy, death or AEs, their missing WOMAC subscale scores after discontinuation will be imputed with values centered at the mean baseline WOMAC subscale score of the treatment group that patient was randomized to. For patients who discontinued treatment due to other reasons, their missing WOMAC subscale scores after discontinuation will be imputed under missing-at-random assumption using the regression method with adjustment for covariates including treatment group, randomization strata (K-L category [2 to 3, or 4] and index joint [knee, hip]) and baseline WOMAC subscale score. Intermittently missing WOMAC subscale prior to treatment discontinuation will be imputed using Markov Chain Monte Carlo method.

Missing data up to week 16 will be imputed 50 times to generate 50 complete data sets by using the SAS procedure PROC MI following the 3 steps below:

- Step 1: The monotone missing pattern is induced by Markov Chain Monte Carlo (MCMC) method in MI procedure using seed number 4751758.
- Step 2: The missing WOMAC subscale scores at visits subsequent to treatment discontinuation will be imputed using the regression method for the monotone pattern with seed number 4751758 and adjustment for covariates including treatment groups, randomization strata (K-L category [2 to 3, or 4] and index joint [knee, hip]), baseline WOMAC subscale score and all WOMAC subscale scores at preceding visits.
- Step 3: For patients who discontinued treatment due to lack of efficacy or AEs, the initially missing and now imputed WOMAC subscale scores at visits subsequent to treatment discontinuation will be adjusted to be centered at the mean baseline value for that treatment group, i.e., final imputed score = imputed score under MAR – (mean change from baseline subscale score at the post-baseline time point for the treatment group based on patients on treatment with non-missing data at that time point).

Each imputed data set will be analyzed using the MMRM with terms for baseline WOMAC subscale score, randomization strata (K-L category [2 to 3, or 4] and index joint [knee, hip]), treatment, visit, and treatment-by-visit interaction as fixed effects. Patients will be included as random effects. The MMRM will be fitted using the MIXED procedure in Statistical Analysis System (SAS) with an unstructured covariance matrix to model the within-patient errors. The denominator degrees of freedom will be estimated using Kenward-Roger's approximation. In the event a model cannot be fitted due to the estimation algorithm failing to converge, the covariance matrix for within-patient errors will be modeled by an autoregressive 1 structure, followed by a compound symmetry structure if convergence is still not achieved for the prior.

The results from the 50 analyses will be combined using Rubin's formulae (PROC MIANALYZE). The least squares means estimates for the mean change from baseline to week 16, as well as the difference of the estimates between fasinumab and placebo will be provided, along with the corresponding standard error, p-value and associated 95% confidence interval. Similar estimates at other visits will also be presented.

The null hypotheses will be rejected when the p-values corresponding to the difference in change from baseline to week 16 between fasinumab 1 mg Q4W and placebo is less than the available $\alpha_0 = 0.05$ for both the WOMAC pain subscale score and physical function subscale score.

For analysis of categorical variables, eg, proportions of patients with $\geq 30\%$ or $\geq 50\%$ improvement in the WOMAC pain subscale scores at week 16, the percentage of patients who are responders based on the Osteoarthritis Research Society International Standing Committee for Clinical Trials Response Criteria Initiative and The Outcome Measure in Rheumatology (OMERACT-OARSI) responder criteria ([Appendix 10.3](#)), the Cochran Mantel Haenszel approach stratified by the randomization strata will be used with missing data considered as non-response.

No control for multiplicity will be made for these analyses. Tests for comparing fasinumab versus placebo will utilize a nominal 2-sided alpha level of 0.05.

Cumulative distribution of percent change from baseline in WOMAC pain and physical function subscale scores will be presented by treatment group. The cumulative distribution plot displays a continuous plot of the percent change from baseline on the X-axis and the percent of patients experiencing that change on the Y-axis. Different responder definitions can be identified along the cumulative distribution curve.

Sensitivity Analysis

Sensitivity analyses will be performed to assess the robustness of the results generated for the secondary efficacy variables.

Analysis of Treatment Policy Estimand

Sensitivity analysis of treatment policy estimand for the secondary endpoints will be performed using similar analysis method as the secondary efficacy analysis. The treatment policy estimand is the difference in means between each fasinumab and placebo in the change from baseline to week 16 in the WOMAC pain and physical function scores in the FAS, regardless of study treatment discontinuation prior to week 16 and regardless of whether or not prohibited medication had been taken. Hence, data from all patients, including data collected after discontinuing treatment up to week 16 will be used in this sensitivity analysis. Missing WOMAC subscale scores up to week 16 will be imputed using the same approach as in Section [5.7.1](#).

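### SAP 5.7.1 Step 3: the adjustment formula does not in general centre lack-of-efficacy and AE dropouts at their arm's mean baseline, although the SAP presents it as doing so

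*SAP*

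**What the plan says.** Protocol 10.4.3 assumes that scores missing after discontinuation for lack of efficacy or AEs return on average to baseline, and it centres the imputed values at the mean baseline. SAP 5.7.1 specifies the mean of the randomized arm. The main analysis sets aside data collected after treatment discontinuation.

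Step 2 imputes under MAR by regression on treatment, strata, "baseline WOMAC subscale score and all WOMAC subscale scores at preceding visits". Step 3 then says that the imputed scores are "adjusted to be centered at the mean baseline value for that treatment group, i.e., final imputed score = imputed score under MAR" minus the arm's mean change at that visit, "based on patients on treatment with non-missing data at that time point". The formula itself begins "final imputed score = imputed score under MAR – (mean change from baseline subscale score". The abbreviation i.e. presents target and formula as the same thing.

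The patient groups also differ slightly. The general rule begins "For patients who permanently discontinued treatment due to lack of efficacy, death or AEs", whereas Step 3 begins "For patients who discontinued treatment due to lack of efficacy or AEs" and so omits death. Week 16 is the tested visit, but "Similar estimates at other visits will also be presented".

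**The concern.** Step 2 carries a patient's own poor or good response into the imputed score. Step 3 then takes off the average change of other patients, those still on treatment. A patient who stopped because nothing improved has an improvement removed that he or she never had, and ends up worse than baseline.

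Two consequences follow. A programmer who implements the sentence and one who implements the formula would produce different data sets for the main analysis of both tested WOMAC endpoints. And a report stating that these patients were centred at baseline would misdescribe what was done.

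**Working it through.** **1. The plan's own figure.** The documents give no number for Step 3. The WOMAC sample size (SAP 2.2: difference 1.1, SD 2.4, two-sided 0.05, 80% power, 15% dropout) reproduces: n = 2 × (1.960 + 0.842)² × (2.4/1.1)² = 74.7, so 75 per arm, and 75/0.85 = 88.2, so 89 against 90 planned.

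**2. Algebra.** For one arm and visit, let B be the arm's mean baseline, C the mean change of on-treatment patients (negative for improvement) and M the mean MAR-imputed score of the affected patients. Step 3 gives a mean of M − C. Its distance from the target is M − C − B, which is zero only if M = B + C, that is, if the affected patients' MAR-predicted level is the arm's average. This needs no assumed numbers.

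**3. Illustration.** Assumed: baseline 6.5 (SD 1.3), mean week-16 change −1.9 on placebo and −3.0 on fasinumab (the gap of 1.1 and SD 2.4 are the SAP's), visit correlation 0.7, two visits seen before stopping, strata left out. Simulated week-16 means (last column computed before rounding):

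| Response before stopping | Arm | B | C | M | M − C | Distance |
|---|---|---|---|---|---|---|
| None | Placebo | 6.50 | −1.88 | 5.65 | 7.53 | +1.03 |
| None | Fasinumab | 6.49 | −3.00 | 5.26 | 8.26 | +1.77 |
| Arm average | Placebo | 6.50 | −1.90 | 4.62 | 6.52 | +0.03 |
| Arm average | Fasinumab | 6.50 | −2.98 | 3.45 | 6.43 | −0.08 |
| 1.5 × average | Placebo | 6.50 | −1.92 | 3.95 | 5.87 | −0.63 |
| 1.5 × average | Fasinumab | 6.50 | −3.03 | 2.69 | 5.72 | −0.78 |

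Patients with no post-baseline score were centred within about 0.15.

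The effect on the week-16 difference (fasinumab minus placebo, so negative favours fasinumab) is each arm's share of non-responding dropouts times its distance:
- 10% in each arm: 0.10 × 1.77 − 0.10 × 1.03 = +0.07.
- 15% placebo, 5% fasinumab: 0.05 × 1.77 − 0.15 × 1.03 = −0.07.
- 5% placebo, 15% fasinumab: 0.15 × 1.77 − 0.05 × 1.03 = +0.21.

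**4. Population-scale runs.** Assumed: baseline 6.5 (SD 1.3), mean changes −2.0 and −3.1, visit correlation 0.6 to 0.9, stop after week 8, lack-of-efficacy dropout 2% to 8%, AE dropout 5% unrelated to response.
- Lack-of-efficacy patients alone land about 0.4 to 2.1 points above the arm's mean baseline. AE patients land close to it.
- The combined group lands about 0.2 to 1.05 above. For example, with 5% of each kind the combined distance is half that of the subset: 0.5 × 0.4 = 0.2 and 0.5 × 2.1 = 1.05.
- The week-16 difference moves 0.03 to 0.09 towards fasinumab at 8% placebo and 2% fasinumab lack-of-efficacy dropout, 0.01 to 0.04 towards it at 5%/2%, and about 0.01 to 0.05 against it at 5%/5%.

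**5. Trial-size runs.** 90 per arm, 600 trials per scenario, 20 imputations, Rubin's rules, unstructured MMRM without Kenward-Roger. The comparator is a Step 2 rewrite that meets the target closely (see the fix). Ranges run over exchangeable correlations 0.6 to 0.9, or 0.6 and 0.9 only when there is no true difference.

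| Lack-of-efficacy dropout, placebo/fasinumab | True difference | Shift | Rejection, SAP | Rejection, comparator |
|---|---|---|---|---|
| 8%/2% | 1.1 | 0.06-0.09 towards fasinumab | 87-88% | 80-82% |
| 5%/5% | 1.1 | 0.03-0.05 against | 74-75% | 77-78% |
| 8%/2% | 0 | 0.07-0.11 towards fasinumab | 4.0-4.5% | 3.3-3.8% |
| 5%/5% | 0 | 0.00 | 2.8-3.2% | 2.5-3.5% |

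The largest shifts are 0.090/0.385 = 0.23 SE with a true difference and 0.110/0.376 = 0.29 SE without one.

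**The case against.** The strongest defence is that the formula is explicit and reproducible, its sign is right, and the consequences are small. Much of this stands. The planned difference is 1.1, and a shift of 0.09 is about 8% of it. The endpoints are secondary. The treatment-policy sensitivity analysis uses observed off-treatment scores, and the protocol asks discontinued patients to keep attending. Every reason-specific dropout rate, correlation and response pattern used above is assumed, because the documents give only 15% dropout overall. AE dropouts who had responded well would land below baseline and could offset the others.

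A reader might infer more than the documents support:
- *That the departure from target is the 0.4 to 2.1 points of the lack-of-efficacy subset.* The protocol and SAP set one target for lack-of-efficacy and AE patients together, so the combined 0.2 to 1.05 is the relevant figure.
- *That every discontinued patient is misplaced.* Patients with no post-baseline score, or whose dropout is unrelated to response, are centred about correctly.
- *That the method favours fasinumab or inflates type I error.* The direction depends on the dropout mix, which the documents do not predict, and rejection without a true difference stayed below 5% in all runs.

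The defence does not remove the mismatch. No other text re-centres the scores, and stopping for lack of efficacy is where an average response is least likely.

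**Conclusion.** Step 3 is wrong as written: the formula is offered as equivalent to a target that it meets only under a special condition. That conclusion rests on the text and algebra alone. The sizes rest on the assumed inputs and are not upper bounds: the pattern of 5% placebo and 15% fasinumab non-responders in the illustration gives 0.21 against fasinumab.

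The main analysis of both WOMAC subscales is affected, and the treatment-policy analysis only for scores still missing. The primary nerve conduction analyses and the responder analyses, which count missing as non-response, are not affected. This should be corrected before unblinding, but it does not threaten the trial's primary objective.

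**What to change.** Keep Steps 1 and 2 and replace the Step 3 formula. Suggested text:

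> For patients who stopped treatment because of lack of efficacy, death or AEs, final score = MAR-imputed score − (A − B). A is the mean MAR-imputed score of these patients in that arm at that visit, averaged over the 50 imputations. B is the arm's mean baseline score.

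This meets the stated target exactly for the combined group, keeps each patient's history, and adds death to match the general rule. Averaging A over the imputations, and not within each one, keeps the between-imputation variance. The week-16 differences were within 0.01 of those from the Step 2 rewrite below.

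The cost is SAP wording and a small programming change, with no new data. There are two downsides. The shift is estimated from few patients: at 7% to 13% affected, 0.07 × 90 = 6.3 to 0.13 × 90 = 11.7 per arm. And lack-of-efficacy and AE patients are centred jointly, not separately.

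A workable alternative is to rewrite Step 2 for these patients so that scores seen before discontinuation leave the model while already imputed later scores stay in, and then to apply the present subtraction. It put the combined group within 0.1 of baseline, but it drops the on-treatment history and needs a separate run per discontinuation visit. The later imputed scores must stay in the model: without them the week 12-16 correlation among lack-of-efficacy patients fell from 0.62-0.91 to 0.09-0.13, and these data feed an MMRM "with an unstructured covariance matrix to model the within-patient errors".

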5.7.2. Subgroup Analysis

Descriptive analyses by treatment group will be performed on both raw and change from baseline values for each visit for the WOMAC pain subscale score and physical function

subscale scores to summarize the treatment effects across subpopulations defined by the following baseline characteristics:

- K-L category [2 to 3, or 4]
- Index joint [Knee, Hip]
- Age group [< 65, 65-74, >=75]
- Sex [Male, Female]
- Weight group [< Median, ≥ Median]
- BMI group [≤ Median, > Median]

Forest plots for the subgroup analysis will be provided.

5.7.3. Analysis of Other Efficacy Variables

Rescue Medications

The percentage of patients who use rescue medication between baseline and Week 16 will be summarized by the treatment group for FAS.

Number of days patients used rescue medication during the treatment period (Day 1 to Week 1, Week 1 to Week 2, Week 2 to Week 4, Week 4 to Week 8, Week 8 to Week 12, Week 12 to Week 16 ...) will be summarized descriptively by treatment group. Weekly average amount of rescue medication use will be summarized by treatment group.

For patients taking rescue medication, weekly average usage of rescue medications (measured in mg) is calculated as follows:

$$= \frac{\text{Total amount of rescue medication used in the specified week (in mg)}}{\text{number of diary entries in the specified week}}$$

Descriptive statistics of the weekly average usage of rescue medications will be presented by treatment group based on the FAS.

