- 1. Patients who discontinue study drug will be encouraged to follow the visit schedule throughout the entire study. If a patient chooses to end study participation he/she will be asked to return to the study site as soon as possible for an early termination visit. Imaging assessments need to be repeated if it has been >30 days since the joints were last imaged. If it has been ≤30 days since imaging assessments were completed, imaging assessments may be completed at the discretion of the investigator.
- 2. HIV and/or hepatitis testing will be performed on a country-by-country basis, according to local guidelines if required by regulatory authorities or ethics boards. Patients must complete all other inclusion/exclusion assessments before undergoing the nerve conduction assessments.
- 3. Only for patients who provide written informed consent for the optional genomics sub-study. The sample should be collected at the day 1 (baseline/randomization) visit, but may be collected at any visit during the study after a patient has been randomized.
- 4. At the screening and pre-randomization visits, study staff will review the "Participating in a Research Study: What You Need to Know" brochure and the "Reporting Your Pain" brochure with patients to ensure they understand what a clinical study is and how to report their pain accurately. At subsequent visits, patients will be asked to review the 'Reporting Your Pain' brochure themselves. At any time during the conduct of the study, patients may require retraining by study staff.
- 5. Study drug administration will be the last procedure at each dosing visit, and will be administered after all laboratory, PK, ADA, and research samples have been collected and all study related activities have been performed. Patients will be observed in the clinic for approximately 1 hour after SC study drug is administered.
- 6. Use of study-provided rescue medication will be recorded daily using diaries. Acetaminophen/paracetamol use will be reported from pre-randomization visit to week 16.
- 7. The WOMAC pain sub-scale will be evaluated for both knees and both hip joints at the screening visit only. Then, the WOMAC Full Survey will be completed only for the index joint at the subsequent visits.

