2.2. Sample Size and Power Considerations

Approximately 180 patients will be randomized in a 1:1 ratio to fasinumab 1 mg Q4W or placebo. With this sample size, the precision of the estimated treatment difference between fasinumab and placebo at week 16 in nerve conduction velocity is no more than 1.21 m/s with a 95% confidence level, assuming a standard deviation (SD) of 3.6 m/s. This sample size provides similar precision for the estimated treatment difference in nerve conduction amplitude assuming

a SD of 3.6 μ V. Assuming a 2-sided alpha level of 0.05 and a 15% dropout rate up to week 16, an enrollment of 90 patients per group will provide at least 80% power to detect an effect size of 0.46 in the Western Ontario and McMaster Universities Osteoarthritis Index (WOMAC) pain and physical function subscale scores (ie, absolute treatment difference of 1.1 between fasinumab and placebo with an SD of 2.4). The assumed treatment difference and SD are based on results from study R475-PN-1227.

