6. DATA CONVENTIONS

The following analysis conventions will be used in the statistical analysis.

For categorical variables, patients with missing data are not included in calculations of percentages unless otherwise specified. When relevant, the number of patients with missing data is presented.

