6.3. Data Handling Convention for Repeat Data

Orthostatic Hypotension data

This applies specifically to the data handling of repeat measurements in the assessment of orthostatic hypotension. Per protocol, if the initial vital assessment for orthostatic hypotension is consistent with the definition of orthostatic hypotension, the supine, standing blood pressure or pulse should be repeated up to 2 more times. The guideline for the repeat assessments are shown below:

Initial Assessment	Repeat Assessment 1	Repeat Assessment 2	Does patient meet OH criteria	Value to be used in the analysis
Does not meet OH definition	N/A	N/A	No	Initial Assessment
Meets OH definition - repeat	Does not meet definition - repeat	Does not meet definition	No	N/A
Meets OH definition - repeat	Does not meet definition - repeat	Meets OH definition	Yes, AE of OH reported	Repeat Assessment 2
Meets OH definition - repeat	Meets OH definition	N/A	Yes, AE of OH reported	Repeat Assessment 1

Baseline for the assessment of orthostatic hypotension vital assessments uses the last available assessment prior to the start of study drug. Measurements post-baseline will not be averaged. Rather frequency counts for patients meeting OH criteria for orthostatic hypotension will reflect the scenario as shown on the table.

Patient reported outcomes data

Should there be duplicate entries for patient reported outcomes data (not including diary data), the average of the entries will be used for questionnaires with numerical values such as the WOMAC. The worst category will be used in the analysis for questionnaires with categorical responses such as the SAS and Joint Pain Questionnaire.

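### Days of rescue use are summarised as raw counts with no diary-day denominator, so unreported days add zero, and the SAP does not say how patients are counted after they withdraw

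*SAP*

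**What the plan says.** SAP 5.7.3 (Rescue Medications) plans three summaries by treatment group: the percentage of patients using rescue up to week 16, the "Number of days patients used rescue medication during the treatment period", and a weekly average amount in milligrams.

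The day count is split into intervals that begin "Day 1 to Week 1, Week 1 to Week 2, Week 2 to Week 4, Week 4 to Week 8" and continue in four-week steps to week 16. It is to be summarised descriptively, and no denominator is given.

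The milligram average is treated differently. Its divisor is the "number of diary entries in the specified week", and it is limited to patients who take rescue.

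The only source for days of use is the diary. Footnote 6 to Table 1 in the protocol states: "Use of study-provided rescue medication will be recorded daily using diaries". Reporting runs from the pre-randomization visit to week 16. SAP 2.2 allows for "a 15% dropout rate up to week 16".

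**The concern.** A raw count of days with use depends on two things: how often the patient took rescue, and on how many days that use could be seen. The planned summary does not separate them. A patient who takes rescue every day but completes the diary on half the days scores the same as a patient who takes it every second day and completes every entry. A patient who leaves early in a four-week interval has only a few days in which to accumulate a count.

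The arm with more withdrawal or poorer diary completion would therefore appear to need less rescue. This matters because rescue use is context for reading the WOMAC results. A smaller consequence is that counts from 7-day and 28-day intervals cannot be compared directly over time.

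**Working it through.** The documents give no expected figure for rescue days, so there is none to reproduce. The check has two parts.

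**1. Does any other rule supply the denominator?**

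- SAP 5 reports n with descriptive statistics, but does not say who belongs to n in a given interval.
- SAP 6 states: "For categorical variables, patients with missing data are not included in calculations of percentages unless otherwise specified". That covers percentages of categorical variables, not counts of days.
- SAP 6.2 and 6.4 deal with missing questionnaire items, dates, laboratory values and the like. Neither has a rule for missed diary days.
- SAP 6.3 has a rule for duplicate patient-reported entries and expressly leaves diary data out of it.
- Protocol 10.4.3 and 10.6 add nothing on days of rescue use.

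No rule was found that changes the raw count.

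**2. How large could the effect be?**

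Inputs from the documents: interval lengths (SAP 5.7.3), a treatment period of 16 weeks = 112 days, and 15% overall dropout (SAP 2.2). Assumptions: rescue on 50% of days in both arms, the diary completion rates shown, and dropout by arm with departures spread evenly over the 112 days.

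*Missed diary days.* Expected count = interval length × daily use rate × share of days reported.

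| Diary completion | Raw count in 28 days | Days with use / diary days |
|---|---|---|
| 100% | 28 × 0.5 × 1.0 = 14.0 | 14.0 / 28.0 = 50% |
| 90% | 28 × 0.5 × 0.9 = 12.6 | 12.6 / 25.2 = 50% |
| 80% | 28 × 0.5 × 0.8 = 11.2 | 11.2 / 22.4 = 50% |

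At 80% completion, a daily use rate of 30% to 70% gives a shortfall of 28 × 0.3 × 0.2 = 1.7 to 28 × 0.7 × 0.2 = 3.9 days.

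*Withdrawal, weeks 12 to 16.* Let d be the share of an arm that leaves by week 16. A quarter of leavers go during the last 28 days and are then seen for 14 of those days on average. Averaged over all leavers, that is 0.25 × 14 = 3.5 observed days, or 1.75 days of use.

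- Leavers scored zero after withdrawal: mean = 14(1 − d) + 1.75d = 14 − 12.25d.
- Leavers dropped from n in later intervals: mean = (14 − 12.25d) / (1 − 0.75d).

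| Dropout in the two arms | Scored zero | Dropped from n |
|---|---|---|
| 15% v 15% | 12.16 v 12.16, difference 0 | 13.70 v 13.70, difference 0 |
| 20% v 10% | 11.55 v 12.78, difference 1.23 | 13.59 v 13.81, difference 0.22 |
| 25% v 5% | 10.94 v 13.39, difference 2.45 | 13.46 v 13.91, difference 0.45 |

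True use is 14.0 days per 28 in every cell, so each difference is false. It does not vanish when leavers are dropped from n, because the interval of withdrawal is still cut short.

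**The case against.** Four points can be made for the plan.

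First, the SAP does not say that missing means no use. A reader might infer that all days after withdrawal count as days without rescue, but no section says so. Because n is reported, a patient with no diary data in an interval could simply be left out. This stands for intervals wholly after withdrawal, where the defect is an unstated rule. It does not help with missed days while the patient is in the study, or with the interval of withdrawal, where the undercount follows from the definition.

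Second, a reader might infer that placebo would be flattered, because placebo patients leave for lack of effect. The documents do not support a direction. Protocol 7.3.2.1 lists reasons for stopping drug, such as adjudicated arthropathy and confirmed neuropathy, that could fall on the fasinumab arm. Protocol 7.3.2 and 8.1.3 also encourage patients who stop drug to remain in the study, so stopping drug need not end the diary.

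Third, the milligram average already has a diary denominator and a weekly unit. That is a partial remedy, but it measures amount rather than frequency and covers only patients who take rescue.

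Fourth, a ratio to diary entries works only if a day without rescue creates an entry. If entries exist mainly on days of use, the ratio drifts towards 100% for every user. Daily recording, and the SAP's own use of entries as a divisor, make this less likely, but the diary design is not shown. The fix should carry that condition.

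**Conclusion.** The point holds in limited form. Followed as written, SAP 5.7.3 undercounts days of rescue use whenever a diary day is missed or an interval is cut short by withdrawal. It also leaves open how later intervals are handled.

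Under the assumptions above, the shortfall is 1.4 to 2.8 days per 28 at 90% to 80% diary completion (14.0 − 12.6 and 14.0 − 11.2). The false difference between arms in weeks 12 to 16 is about 0.2 to 1.2 days at 20% v 10% dropout. Taking 14 × 0.90 − 14 × 0.80 = 1.4 days as the withdrawal effect would go too far. That figure needs every leaver to be gone before week 12 and scored zero, whereas the planned 15% is cumulative to week 16. With equal dropout and equal completion both arms are too low, but no difference between them is created.

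The use rate, diary completion and dropout by arm are assumptions; the documents give only the overall 15%. Days of rescue use is a descriptive variable with no planned test, so this is a minor improvement to the plan.

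**What to change.** In SAP 5.7.3, define for each patient and interval:

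100 × (distinct days with rescue use) / (days with a diary entry, including entries of no use).

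Show the number of diary days by arm and interval. Set the value to missing, not zero, when an interval contains no diary day; this also settles who is in n after withdrawal. Count distinct days, because the diary records use for OA pain and for other pain (Protocol 7.7.2).

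Before adopting this, confirm that the diary records days without use. If it does not, use the patient's days in the study within the interval as the denominator. That corrects for withdrawal and unequal interval lengths, but not for missed entries.

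The cost is SAP wording and a different divisor on data already collected. Values will be noisier for patients with few diary days, which the display of diary days makes visible. The ratio also assumes that skipped days resemble reported days.
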